This study will provide rigorous epidemiologic evidence regarding the influence of fetal exposure to HIV and ART on developmental and mental health outcomes from infancy to adolescence, including obtaining a national population-based estimate of HEU burden of developmental and mental health outcomes and strategies for programmatic surveillance and referral.

11. Specific aims and hypotheses

Aim 1: Within a longitudinal cohort of 1000 HEU and 1000 HUU infants enrolled at 6 weeks of age from 5 MCH clinics and followed 6-monthly:

HOPE study protocol

Version 1.3

July 21, 2020

Aim 1a. To compare HEU and HUU infants and children for growth, hearing, and neurodevelopmental outcomes; and determine influence of ART timing/regimen on HEU outcomes. To determine whether fetal HIV/ART exposure impacts 4-year neurodevelopmental outcomes; and assess impact of peripartum ART regimen and timing.

Aim 1b: To compare telomere length in HEU and HUU and determine associations with neurodevelopmental outcomes.

Aim 2a: To determine the impact of HEU and HUU status, as well as maternal peripartum ART, on neurodevelopment and mental health (ASD, ADHD, depression, and anxiety). We will pilot a mobile screening strategy to detect adverse neurodevelopmental and mental health outcomes in HEU for use in large-scale screening in Aim 2b. Mothers attending HIV care will be invited to bring their HEU (aged 3-18) (200 HEU, 50 per age-stratum: 3-6, 7-10, 11-14, 15-18) for screening; age- matched HUU will be recruited from the community.

Aim 2b. To estimate population-burden and cofactors of adverse neurodevelopmental and mental health outcomes in HEU using mobile teams to screen HEU in ~100 large HIV Care Clinics throughout Kenya (4000 HEU; age-stratified, 3-6, 7-10, 11-14, 15-18) and 400 age-stratum matched community HUU.

Aim 3. To estimate the cost of this screening strategy and convene stakeholders to review data regarding programmatic integration of HEU screening.

12. Study design and methodology

a. Study area description

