Cross-sectional surveys. These will be done in 2 phases 1) Pilot phase and 2) Population phase. The pilot phase will be conducted in one facility (Rachounyo sub-County hospital) after which we will begin population based assessments in 100 large HIV clinics. Procedures for enrollment and assessment are similar for 2 phases.

HOPE study protocol

Version 1.3

July 21, 2020

ii. Study populations

HEU and HUU caregiver-child pairs

iii. Recruitment procedures

MLHIV attending HIV Care clinics will be asked about potentially eligible HEU children aged 3-18 by study nurse. MLHIV who are interested in participating will be invited to return with their child/adolescent for participation in the study. Study nurses will also liaise with clinic community health workers (CHWs) to recruit eligible HUU in the relevant age strata (3-6, 7-10, 11-14, 15-18 years) in the community. CHWs will invite mothers of eligible HUU children to participate in the study for evaluation and mother-child/adolescent pairs will be enrolled at a neutral site (typically MCH or family planning [FP] clinic) or at home. Study nurses will be accompanied by the community health worker for home enrollments. A standard recruitment form will be used.

The target enrollment is 400 children and adolescents (200 HEU and 200 HUU) in the pilot phase and 4400 (4000 HEU and 400HUU) age 3-18 years (stratified to the following groups: 3-6, 7-10, 11-14, 15-18 and by HIV status (HEU or HUU)) in the population phase. The pilot phase will be conducted in one facility in rural Kenya (Rachuonyo Hospital HIV clinic), and the population phase in 100 large HIV care clinics with at least 1000 adult women in HIV care.

For HEU, caregivers attending HIV clinics who have children in the proposed age-groups will be recruited by the clinic staff. Caregivers who are interested will meet with the study nurse and be provided with details on the study and study procedures and invited to bring children for enrollment. All study procedures will be completed at enrollment with no follow-up procedures.

HUU will be recruited from the neighboring community around the HIV Care Clinic from where the HEU are recruited. Nurses and Community health workers (CHW) will visit households to recruit interested caregivers of children age 3-18 and enroll those who meet eligibility criteria and are willing to confirm HIV status (using HIV self-test kits) and enroll their children in the study.

Eligibility criteria

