R33 Aim 2				
Difference in BENC1 scores	0.29	1000 HEU: 100 HUU age stratum (7-11yo)		SD=1.0
Difference in ADHD prev.	7.7%	1000 HEU: 100 HUU		2.7% in HUU ¹⁷⁵
Difference in depression prev	10.1%	1000 HEU: 100 HUU per age stratum		HUU 10%

Analyses: For binary outcomes such as ADHD and depression, multivariate generalized linear models (GLM) with log link and binomial family for relative risk estimation clustered by site will be used. For continuous variables such as NIH-Toolkit, we will use multivariate GLM with Gaussian family and identity link. As previously noted in Aim 1, we will include *a priori* potential confounders - maternal depression, preterm birth, and infant birthweight - in multivariate analysis, after assessment of collinearity.

MDAT (social, fine motor, gross motor, language)	GLM
Hearing	GLM
BENCI (processing speed, visual-motor coordination, attention, language, memory, executive function)	GLM
SDQ total domain score	GLM
ADHD screen (analyze positive SNAP-IV and subset validated on MINI-Kid)	GLM
PHQ-9 (prevalence of moderate-severe symptoms)	GLM
Neuropsychiatric diagnoses	GLM

Training procedures for aim 1 and 2

The study team will develop protocols and training materials for clinic staff. A 5-day training workshop will be designed. The package will include the basics of early childhood development, pediatric mental health, screening and use of the study screening and diagnostic tools. The training will cover neurodevelopmental assessments, psychometric testing, and administration, scoring and interpretation of the MDAT and NIH Toolbox. The 5-day nurse training workshop will cover general sensitization to the testing situation, including ensuring that the child follows the instructions, methods of cross-checking to determine whether a child understood instructions, learning when to give breaks, how to re-engage the child and how to react to distress. The training will cover how to recognize need for referrals and provide motivational interviewing and culturally sensitive assessment skills. To ensure quality control, the study coordinator will conduct refresher training for staff to ensure operating procedures are followed consistently. We will also develop checklists for tests requiring multiple tests as well as the use of tablet based tests to ensure quality assessments.

e. Aim 3

i. **Study design**

This Aim of the study involves 2 cross-sectional components:

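### Aim 2b is presented as a national population-based burden estimate, but its frame is eligible HEU children reached by invitation through 100 large HIV clinics, and it cannot support that claim

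*Protocol*

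**What the plan says.** The Rationale (section 10) lists among the study's products: "including obtaining a national population-based estimate of HEU burden of developmental and mental health outcomes". Aim 2b in section 11 repeats the ambition: "To estimate population-burden and cofactors of adverse neurodevelopmental and mental health outcomes in HEU". The front summary table and section 12.d also call this phase population based.

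The design that is to deliver it is set out as follows.

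- **Clinics** (section 12.d.iii): "100 large HIV care clinics with at least 1000 adult women in HIV care". No rule for selecting the 100 is given.
- **Families** (section 12.d.iii): mothers with HIV, or caregivers, who attend these clinics are asked about children in the age range and invited to bring them. No probability sampling is described.
- **Children** (section 12.d, Eligibility criteria): the child must be healthy (not defined) and HIV negative. For HEU, the timing of the mother's HIV diagnosis and ART must be known.
- **Sample** (section 11, Aim 2b): "4000 HEU; age-stratified, 3-6, 7-10, 11-14, 15-18". The split of the 4000 appears only in the detectable-effect table of section 12.d.vii: "1000 HEU: 100 HUU per age stratum".
- **Analysis** (section 12.d.vii): for binary outcomes, a model with "log link and binomial family for relative risk estimation clustered by site". How a burden estimate is to be calculated is not stated.

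Section 16 discusses limitations of the Aim 1 cohort only.

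**The concern.** A national population-based estimate needs every HEU child in the target population, or at least every type of clinic and family, to have some chance of selection. Here three layers of restriction apply: clinic size, a caregiver who attends, and the eligibility criteria. The undefined health criterion matters particularly in a burden survey, because it could remove some of the affected children whose number is wanted.

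The result has a use. Under Aim 3, burden findings go to policy makers at the stakeholder workshop as input to a possible HEU screening programme. A figure for eligible children of attenders at large clinics, labelled national, would be applied to children whom the survey could not have reached.

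A second, conditional matter follows. If the HEU sample is filled equally across the age strata, any single all-age prevalence takes its age mix from the sampling plan unless it is standardised.

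**Working it through.** **1. Claim against frame.** The claim covers HEU burden in Kenya. The frame covers HEU aged 3-18 who are healthy, have documented or reported maternal HIV and ART timing, and have a caregiver attending one of 100 clinics with 1000 or more women in care. Children whose families use only smaller clinics, or have nobody in care at these clinics, have inclusion probability zero. A weight is the inverse of an inclusion probability, so none exists for them. An analysis plan written later cannot restore them.

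**2. What the clinic restriction could do.** The protocol gives neither the share of HEU children served by large clinics (s) nor prevalence inside (P_L) and outside (P_O) them, so all three are assumed here.

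National prevalence = s·P_L + (1 − s)·P_O. Error if P_L is reported as national = (1 − s)(P_L − P_O).

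| s | P_L | P_O | National | Error (points) |
|---|---|---|---|---|
| 0.3 | 10% | 8% | 8.6% | +1.4 |
| 0.3 | 10% | 13% | 12.1% | −2.1 |
| 0.5 | 10% | 8% | 9.0% | +1.0 |
| 0.5 | 10% | 13% | 11.5% | −1.5 |
| 0.7 | 10% | 8% | 9.4% | +0.6 |
| 0.7 | 10% | 13% | 10.9% | −0.9 |

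The error is zero if prevalence does not differ by clinic size.

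**3. Stratum sizes.** The plan gives no precision figure for burden, so the only figures to reproduce are the Aim 2 detectable effects. Two-sided alpha 0.05 and 80% power are assumed to carry over from Aim 1. For the cognitive score with 1000 HEU and 100 HUU (HIV-unexposed uninfected), SD 1.0: (1.960 + 0.842) × √(1/100 + 1/1000) = 2.802 × 0.1049 = 0.294, against 0.29 stated. For ADHD the same approach gives 7.67 points, against 7.7 stated. The depression row does not reproduce (10.97 against 10.1 points), but that has no bearing here. The sizes add up: 4 × 1000 = 4000 HEU and 4 × 100 = 400 HUU. The table therefore implies equal strata, as the pilot states outright: "200 HEU, 50 per age-stratum: 3-6, 7-10, 11-14, 15-18".

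**4. What equal strata would do to an all-age figure.** The protocol gives no HEU age distribution and no age-specific HEU prevalence. Assume prevalences of 5, 8, 12 and 18% across the four strata.

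Equal strata: (5 + 8 + 12 + 18)/4 = 10.75%.

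| Assumed HEU age shares | Standardised prevalence | Shift of the equal-strata figure (points) |
|---|---|---|
| 40/30/20/10 | 2.0 + 2.4 + 2.4 + 1.8 = 8.60% | +2.15 |
| 35/30/20/15 | 1.75 + 2.4 + 2.4 + 2.7 = 9.25% | +1.50 |
| 30/27/23/20 | 1.5 + 2.16 + 2.76 + 3.6 = 10.02% | +0.73 |
| 20/25/27/28 | 1.0 + 2.0 + 3.24 + 5.04 = 11.28% | −0.53 |

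For scale, the simple 95% half-width at n = 4000, before clustering, is 1.96 × √(0.1075 × 0.8925/4000) = 0.96 points. The shift is zero if prevalence is flat across age or the age shares are equal. Stratum-specific prevalences do not carry it.

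**The case against.** The strongest reply is that the frame is disclosed. Aim 2b itself says that the survey uses large HIV clinics across Kenya, so a reader can see what was sampled, and the geographic spread is real. If 100 clinics were nearly all those above the threshold, the missing selection rule would matter little. This is fair, but disclosure in one section does not make the claim in another correct, and section 16 leaves the gap unacknowledged.

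A reader might also infer that the overall burden figure will simply reflect fixed age quotas, from an unweighted model that counts each clinic equally. The document does not support that reading:

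- No pooled 3-18 prevalence is expressly planned. Section 9 stresses adequately powered age strata, the Aim 2 table works by stratum for some outcomes, and most instruments in section 12.d.vi cover only part of the age range.
- The protocol is silent on weights. The named model estimates relative risks, not burden, and weighting or standardisation may properly sit in an analysis plan that is not at hand.
- 4000/100 = 40 per clinic is an average. No per-clinic allocation is stated.
- 1000 HEU per stratum appears only in the detectable-effect table. The Aim 2b text says only that the sample is age-stratified.

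Nor can one say that children whose mothers have died are all excluded, because section 12.d.iii refers to caregivers as well as mothers. Finally, every magnitude above rests on assumed inputs, and the sign changes with them.

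**Conclusion.** The point holds as a mismatch between claim and frame. Section 10 attributes to the survey a national, population-based property that section 12.d does not give it, and no later analysis can supply that property for children with no chance of inclusion. This conclusion rests on protocol text alone and needs no assumed number.

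The size of any error is unknown from the document. The figures of −2.1 to +1.4 points for the clinic restriction and −0.5 to +2.2 points for the age mix only show that errors of one to two times the simple half-width are possible. The age-mix part is conditional: it arises only if an all-age figure is reported without standardisation, prevalence varies with age and the HEU age shares are unequal.

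**What to change.** 1. In sections 10 and 11, restate the Aim 2b target as eligible HEU aged 3-18 reached through HIV clinics with 1000 or more women in care, and drop the national population-based description.
2. State in section 12.d.iii how the 100 clinics are chosen.
3. Add the restricted frame to section 16: large clinics only, attending caregivers, recruitment by invitation, and the eligibility limits on child health and maternal records.
4. Name age-stratum prevalences as the main burden result.
5. If an all-age figure is given, standardise it to the HEU age distribution and weight it by clinic size where counts can be obtained.

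Items 1 to 4 are wording and leave sample size and procedures unchanged. Their price is a narrower stated scope. Item 5 needs counts. Section 9 reports family-tree cards in adult records and earlier EMR extraction from about 100 clinics, which is encouraging. It also reports that only 62% of adults in care in one study had all their children tested, and that some children tested were born before maternal infection. The counts would therefore need work before they gave an HEU age distribution. Weighting also widens the interval. With equal strata, the approximate variance factor is 4 × Σ(share²): 1.20 for shares 40/30/20/10 and 1.02 for 30/27/23/20, so about 10% and 1% wider. Clinic-size weights would add to that.

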For all aims, the study nurse will provide an in-depth explanation of the purpose and procedures of the study, in the language of the woman's choosing, answer any questions the woman may have, and invite the woman to participate in the study. Mothers will be informed that their participation is voluntary and that participation or nonparticipation in the study will in no way alter the nature of health care services that they receive. If interested in participating, the study nurse will screen HEU and HUU mother-infant pairs for eligibility, and, if eligible, woman will provide written consent for enrollment. If the participant is not literate, a witness unrelated to the study will be present and the consent will be read aloud. The participant will provide oral consent with a witnessed thumbprint documented as consent. This system of recruitment has been highly successful in past and ongoing studies conducted by the research team.

HOPE study protocol

Version 1.3

July 21, 2020

Eligibility criteria

Inclusion criteria:

- Infant age 6 weeks (+/- 2 weeks)
- Healthy infant as determined by study nurse
- Mother age ≥ 18
- Planning to remain in study catchment area for 4 years

Exclusion criteria:

- Infant HIV positive
- Mother HIV status unknown (determined using mother-baby maternal and child health booklet)
- Caregiver planning to relocate

iv. Enrollment and study procedures

Data: At enrollment, contact information, maternal sociodemographic characteristics, adverse childhood events (ACEs), depression (maternal PHQ9), obstetric and medical history, and infant birth history and anthropometrics will be assessed. Medical records from MCH/CCC and viral load records will be abstracted from existing data sources. Maternal HIV status will be determined using mother-baby maternal and child health booklet; if the mother has not been tested for HIV, she will be offered HIV testing.

At every visit, study staff will perform anthropometric measurements (height/weight/head circumference, MUAC), neurodevelopmental and mental health assessments, and collect data on past and current child comorbidities and nutrition.

Summary of procedures for recruitment and enrollment

1. MCH nurse reads recruitment script to potential participant
2. MCH nurse refers interested participant
3. MCH nurse documents reason for declining to participate
4. Study nurse assesses eligibility
5. Study nurse gives more information on the study

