6. Interested mothers give informed consent to participate
7. Study staff conduct HIV testing for mothers if HIV status not available in mother-baby maternal and child health booklet
8. Study staff collect contact and locator information
9. Study staff collect enrollment data - demographics, HIV status, pregnancy history, ART use and history
10. Study staff conduct anthropometric measures, neurodevelopmental and mental assessments, hearing tests on infant and collect DBS
11. Study staff reimburse client and give appointment for the next visit

v. Laboratory methods

Blood samples: Dried blood spots (DBS) for assessment of telomere length will be collected at enrollment and 12 monthly either using finger prick or venous blood draw (0.5ml).

vi. Data collection instruments

Socio-demographic, pregnancy and post-partum data: Socio-demographic information, family characteristics, medical history (including HIV status), mental health history and substance use history will be collected from caregivers. We will assess for caregiver depression at every visit using PHQ-9.

Growth assessments: Standard anthropometric measures including weight, height/length, head circumference and mid-upper arm circumference will be assessed by trained study staff. These measures will be converted to standard Z-scores using the WHO growth standards.

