Screening for child mental health conditions. The Strengths and Difficulties Questionnaire¹³¹ is a 25-item scale widely used as a screening tool for mental health in numerous LMIC settings¹³², including SSA¹³³. The SDQ will be used beginning at age 3. The SDQ includes 4 difficulty scales (emotional symptoms, conduct problems, hyperactivity/inattention, and peer relationship problems) and a scale for prosocial behavior. The Strengths and Difficulties Questionnaire¹³¹ is a 25-item scale widely used as a screening tool for mental health in numerous LMIC settings¹³², including SSA¹³³. The SDQ will be used beginning at age 3. The SDQ includes 4 difficulty scales (emotional symptoms, conduct problems, hyperactivity/inattention, and peer relationship problems) and a scale for prosocial behavior. SDQ scales had good internal consistency in African studies¹³⁵⁻¹³⁹, although the hyperactivity/inattention scale has performed less well¹³⁸. Poor SDQ scores correlated with expected demographic characteristics in South Africa and Uganda¹³⁷. A z-score corresponding to the 80th-90th and >90th percentiles have been considered borderline and indicative of 'caseness'¹³⁶, and will prompt further screening.

Hearing: We will use combined otoacoustic emission (OAE) and auditory brainstem response (ABR) screening tests to assess hearing. Infants will be screened at 6 weeks using OAE and referred for ABR if they screen positive. At age 3 and 4 years, we will use a smart phone based hearing screen (Hearscreen TM) to assess hearing. These tests are non-invasive and does not involve input of energy into the body.

Summary table for aim 1 data collection

	Enrollment	Month 6	Month 12	Month 18	Month 24	Month 30	Month 36	Month 42	Month 48
Consent	X								
Locator data	X	X	X	X	X	X	X	X	X
Medical history	X	X	X	X	X	X	X	X	X
Anthropometry	X	X	X	X	X	X	X	X	X
MDAT	X	X	X	X	X	X	X	X	X
SDQ							X	X	X
ASD screen				X	X				X
Hearing screen	X						X		X
DBS	X		X		X		X		X

vii. Sample size determination & data analysis

For **all analyses**, *a priori* cofactors of interest in the multivariate analysis include household sociodemographic factors, birthweight, preterm birth, maternal depression, infant sex, maternal education, and infant/child LAZ. Collinearity will be examined using standard error assessments and multivariate models will include non-collinear variables associated with growth in univariate model ($p < 0.05$).

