Mortality, infectious morbidity, and hospitalizations: Cox regression will be used to compare survival of the HEU and HUU cohorts and to determine predictive factors for mortality overall and stratified by HEU/HUU. During the 4-year follow-up period for the aim 1 cohort, incidence of hospitalization, severe pneumonia, and diarrhea will be calculated and compared between HEU and HUU cohorts as number of events over person-time of follow-up with censoring for mortality and loss to follow-up. Predictors of first morbidity (separate analyses for pneumonia, severe diarrhea, and hospitalizations) will be identified using Cox proportional hazards regression with censoring for mortality and loss to follow-up.

Analysis: We will compare MDAT social, motor and language scores and prevalence of ASD between HEU and HUU and among HEU by maternal VL detection in pregnancy, maternal pre-conception ART, and by ART regimen. The percentage of normal, borderline and high scores on the SDQ will be calculated for the domains: emotional problems, conduct problems, hyperactivity, peer problems, and prosocial behavior and for total difficulty. Univariate and multivariate logistic regression will be used to determine whether HEU vs. HUU is associated with higher likelihood of high scores on SDQ domains overall. Among HEU, we will assess influence of maternal VL, ART, and regimen. Multivariate analyses will be adjusted for maternal sociodemographic factors and depression and infant birthweight and growth.

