Child or adolescent age 3-18 years

Child/adolescent is healthy and HIV negative

Mother HIV status known

Mother HIV diagnosis and ART timing known (for HEU)

Caregiver \geq 18 years willing to take children to clinic for evaluation

iv. Enrollment and study procedures

Enrollment will be conducted at a neutral location (typically public MCH clinic) or at home. No additional visits will be conducted after enrollment.

Determination of HIV status for HEU and HUU: A combination of medical records and HIV testing will be used to determine HIV status of mothers and children. Maternal HIV-positive status during the pregnancy with each child will be determined first using the mother-baby maternal and child health booklet; in the event that this

HOPE study protocol

Version 1.3

July 21, 2020

booklet is not available, records from the HIV care clinic documenting the date when the mother was diagnosed with HIV or started ART will be used (only for HIV positive mothers). In the event of no records are available, maternal report of being diagnosed with HIV either during or prior to the pregnancy with each child will be used (only for HIV positive mothers). For mothers who report not being HIV positive at the time of pregnancy and for whom mother-baby maternal and child health booklets are not available, we will offer maternal HIV testing; mothers who do not consent to HIV testing will not be enrolled.

For HEU dyads, children's HIV negative status will be determined using the same set of procedures (first reviewing mother-baby maternal and child health booklet, then infant HIV testing history records); if the child has not been tested for HIV after the cessation of breastfeeding, HIV testing will be offered for the child. Children ages 7-14 years will be asked to provide assent without mention of HIV; children ages 15-18 will be asked to provide assent (or consent for 18 year olds) with explicit mention of HIV testing and will be told that they can choose whether they wish to share their results with their caregivers. If children decline HIV testing, they will not be enrolled in the study.

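### Aim 1 specifies no infant HIV test or record check after the 6-week exclusion, and no rule for infants infected during follow-up

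*Protocol*

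**What the plan says.** All references are to the Protocol.

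- **Entry (12.c.iii, Eligibility criteria).** "Infant HIV positive" is an exclusion, applied at 6 weeks of age with a 2-week margin either side. The text does not say how the infant's status is established.
- **HIV testing in Aim 1 (12.c.iv, summary of procedures).** The only test is of mothers, at enrolment: "Study staff conduct HIV testing for mothers if HIV status not available in mother-baby maternal and child health booklet".
- **Blood samples (12.c.v; also the summary table in 12.b).** "Dried blood spots (DBS) for assessment of telomere length will be collected at enrollment and 12 monthly". No other use is given.
- **Visit schedule (12.c.vi, summary table for Aim 1 data collection).** There is no HIV row from enrolment to month 48. "Medical history" is marked at every visit.
- **Caregiver-reported data (12.c.vi).** Caregivers give "medical history (including HIV status" among other items, without a statement of whose status is meant. Child comorbidities are also recorded at every visit (12.c.iv).
- **Time-to-event analysis (12.c.vii).** "Cox regression will be used to compare survival of the HEU and HUU cohorts". Censoring for the morbidity outcomes is for death and loss to follow-up.
- **Aim 2 (12.d.iv).** For HEU children, "if the child has not been tested for HIV after the cessation of breastfeeding, HIV testing will be offered for the child". A child who declines is not enrolled.

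**The concern.** The study asks what exposure to HIV and antiretroviral treatment does to children who are not themselves infected. In an exposed infant who is still breastfed, a negative status at 6 weeks does not settle that question. Aim 2 recognises this and Aim 1 does not, although both use the same HEU label.

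Infection after enrolment can occur only in children who count as HEU, apart from the rare HUU mother who is infected later. Children with HIV do worse on the study's outcomes: Table 2 gives baseline developmental z-scores of -0.55 to -1.02 in children with HIV starting treatment. Infected children who stay in the HEU group therefore push later HEU v HUU contrasts in the direction the study expects to find.

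Contrasts within HEU by maternal viral load could be affected more, if infections cluster among infants of viraemic mothers.

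The gap lies in data collection. An analysis plan can censor or exclude at infection only if results and dates were recorded.

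**Working it through.** **1. The plan's own figure.** Inputs from the effect-size table in 12.d.vii: 1000 per group, SD 1.0, 80% power, alpha 0.05 (taken as two-sided). Detectable difference = SD × √(2/n) × (1.960 + 0.842) = 1.0 × √(2/1000) × 2.802 = 0.125, stated as 0.13. With 800 per group (20% attrition) it is 0.140, stated as 0.14. Both reproduce.

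**2. Shift in the MDAT mean.** Let f be the share of HEU infants infected after enrolment and D the deficit of infected children in SD units. With no true HEU effect, the spurious difference is f × D. The protocol gives no value for f, so f = 1-3% is an assumption. D = 0.5-1.0 roughly spans the Table 2 scores, which are relative to a Malawian norm and not to a concurrent uninfected group. The false-positive rate is P(|Z| > 1.96) when Z has mean f × D / SE and SE = √[(1 + 1 + f(1 - f)D²)/1000].

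| f | D | Shift (SD) | Share of 0.13 | False-positive rate |
|---|---|---|---|---|
| 1% | 0.5 | 0.005 | 4% | 5.1% |
| 1% | 1.0 | 0.010 | 8% | 5.6% |
| 2% | 1.0 | 0.020 | 15% | 7.3% |
| 3% | 1.0 | 0.030 | 23% | 10.2% |

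As a stress case, f = 5% with D = 1.0 gives 0.05 SD and 19.7%.

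**3. Apparent mortality ratio.** Let m0 be 4-year mortality in HUU and in truly uninfected HEU, and mi that in infected children. The ratio is [(1 - f) × m0 + f × mi] / m0. All three inputs are assumptions: f = 1-3%, mi = 20-30%, m0 = 2-4%.

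- Low end (1%, 20%, 4%): (3.96% + 0.20%) / 4% = 1.04. Infected children supply 0.20/4.16 = 5% of HEU deaths.
- Middle (2%, 30%, 3%): (2.94% + 0.60%) / 3% = 1.18. Share of deaths 0.60/3.54 = 17%.
- High end (3%, 30%, 2%): (1.94% + 0.90%) / 2% = 1.42. Share of deaths 0.90/2.84 = 32%.

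With 1000 per group and SE(log ratio) ≈ √(1/d1 + 1/d0), where d1 and d0 are the deaths in each group, the false-positive rates are about 5%, 10% and 22%. In the middle case there are about 30 + 35 = 65 deaths, and the detectable hazard ratio is about exp(2 × 2.802/√65) = 2.0.

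**4. Contrast within HEU by maternal viral load (illustration only).** Assume 20 infected among 1000 HEU, 15 of them among 200 infants of viraemic mothers and 5 among the other 800. With D = 1.0 the spurious gap is 15/200 - 5/800 = 0.075 - 0.006 = 0.069 SD. The detectable difference for 200 v 800 is 2.802 × √(1/200 + 1/800) = 0.22, so the gap is about 31% of it.

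**5. Precision cost of removing infected children.** Dropping 50 of 1000 HEU gives 2.802 × √(1/950 + 1/1000) = 0.127, against 0.125.

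**The case against.** A reader might infer that Aim 1 never re-checks infant status. The text does not go that far. History taken from caregivers includes HIV status, medical history is scheduled at every visit, and child comorbidities are recorded, so a known diagnosis could surface. This stands. But the text does not say that the child's status is meant, asks for no result or date, and gives no rule for using the information.

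A reader might also infer that infected children will be analysed as HEU. The protocol does not say that grouping is as enrolled. HEU means uninfected, and the statistical analysis plan, which is not shown, may define analysis sets and censoring. That stands for the handling rule. It does not cure the missing ascertainment.

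Nor is every contrast affected. Baseline MDAT, the first hearing screen and 6-week telomere length are measured before any later infection. Later telomere length cannot be said to suffer more than MDAT: it is also compared by linear regression, its detectable difference is larger (0.18 with 500 per group), and 12.c.vii cites one study with no difference by HIV status. Effects on hospitalisation and severe infection cannot be sized from the document.

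The mortality figures rest wholly on assumed rates, mortality is a secondary outcome (Table 6), and a spurious ratio of 1.18 would usually not reach significance. Section 16 expects all HEU mothers to have started treatment before or during pregnancy, which argues for the lower end of f. Undetected infection in the HUU group, whose mothers are not re-tested, would act in the opposite direction. Finally, Aim 2 applies the post-breastfeeding standard to HEU children only; HUU children under 15 are taken as negative from the mother's result.

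**Conclusion.** The concern holds as a gap in ascertainment. Aim 1 specifies no infant test or record check after the enrolment exclusion and no rule for a child infected later, while Aim 2 applies a stricter standard to the same label. The direction of bias for HEU v HUU contrasts after enrolment is toward the hypothesised harm.

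The size cannot be had from the document. At an assumed 1-3% infected it is small for the primary MDAT outcome (0.005-0.03 SD against a detectable 0.13). It ranges from negligible to material for mortality (ratio 1.04-1.42, on assumed death rates and no true effect). The contrast by maternal viral load may be more exposed, but only if infections cluster among viraemic mothers. The documents do not support the view that the main result is seriously compromised. The change is worth making because it is cheap and because results and dates not collected during follow-up may not be recoverable at analysis.

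**What to change.** 1. State in 12.c.iii or 12.c.iv how infant HIV status is established at entry.
2. Add one item to the follow-up visits for HEU infants: abstract routine infant HIV results and dates from the MCH and HIV care clinic records already used at enrolment. Continue until a result after the end of breastfeeding is on record. Say explicitly that the HIV status item in the caregiver history includes the child's.
3. Pre-specify handling in the HEU v HUU analyses. Censor time-to-event outcomes at the first positive result, and exclude MDAT, growth and telomere values from that date on. Keep the as-enrolled grouping as a sensitivity analysis.

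The cost is one abstraction item per visit, a short addition to the analysis section, and the loss of a few HEU observations. Even 50 lost of 1000 moves the detectable MDAT difference only from 0.125 to 0.127. No new study test is required. One limit remains: a child who dies or leaves before a routine test stays unclassified, so the number of HEU infants without a result after breastfeeding should be reported.
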